4.4.4 Analysis of the Secondary Efficacy Endpoints

4.4.4.1 Analysis of NPR, BOR, ORR and CBR

The secondary endpoints NPR at 24 weeks, BOR, ORR and CBR based on RECIST v1.1, as well as mBOR based on modified RECIST, will be analyzed using standard 95% (exact binomial, two-sided) confidence intervals for proportions.

4.4.4.2 Response and lesion assessments

A swimmer plot will be provided to illustrate the response assessments over time, and a spider plot will be presented to show the change in sum of target tumor diameters (SLD) over time. A waterfall plot will show best SLD change from baseline.

4.4.4.3 Time to event analyses

The time-to-event variables PFS, OS, TTP and DOR will be presented graphically using the Kaplan-Meier (KM) approach. The median survival time and its 95% confidence interval will be presented. Additionally, the estimated survival rate together with its associated 95% confidence interval at 24 weeks, at 6 and 12 months, and at 24 months (for OS only) will be presented.

Duration of response will be evaluated only for patients who achieve CR or PR (and only analysed if there are more than 3 such patients in a cohort).

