Appendix 1 Schedule of Assessments

	Screening ¹	Treatment (All cycles, unless otherwise indicated) ²	Treatment discontinuation visit	Follow-Up	End of Study Visit
Day (Window)	Days -35 to -1	Day 1 (\pm 3 days for cycles \geq 2)	\leq 30 days after last dose	Every 3 months from study treatment discontinuation (\pm 30 days)	24 months
Informed consent ¹	X				
Review of eligibility criteria	X				
Medical history and demographics ³	X				
Cancer history ⁴	X				
Concomitant medications ⁵	X	X	X		
Tumor assessment RECIST 1.1 and modified RECIST per Appendix 3⁶	X	Every 6 weeks, \pm 5 days (2 cycles) for the first 24 weeks and every 12 weeks, \pm 5 days (4 cycles) thereafter until loss of clinical benefit, withdrawal of consent, death, or study termination by the Sponsor, whichever occurs first			
Brain MRI/CT Scan with contrast ⁶	X				
Specific tumor markers ⁷	X	As clinically indicated, but at least every 6 weeks, \pm 5 days (2 cycles) for the first 24 weeks and every 12 weeks, \pm 5 days (4 cycles) thereafter until loss of clinical benefit, withdrawal of consent, death, or study termination by the Sponsor, whichever occurs first			
Collection of results from specific markers assessed on tumor tissue ⁸	X				

Appendix 1

Schedule of Assessments (cont.)

	Screening ¹	Treatment (All cycles, unless otherwise indicated) ²	Treatment discontinuation visit	Follow-Up	End of Study Visit
Day (Window)	Days –35 to –1	Day 1 (\pm 3 days for cycles \geq 2)	\leq 30 days after last dose	Every 3 months from study treatment discontinuation (+/- 30 days)	24 months
Physical examination ⁹	X	X	X		
ECOG performance status	X	X(-3 days from treatment start)	X		
Vital signs ¹⁰	X	X	X		
Oxygen saturation (pulse oximetry)	X	X	X		
12-lead electrocardiogram ¹¹	X	X	X		
Weight	X				
Height	X				

Appendix 1

Schedule of Assessments (cont.)

	Screening ¹	Treatment (All cycles, unless otherwise indicated) ²	Treatment discontinuation visit	Follow-Up	End of Study Visit
Day (Window)	Days -35 to -1	Day 1 (\pm 3 days for cycles \geq 2)	\leq 30 days after last dose	Every 3 months from study treatment discontinuation (+/- 30 days)	24 months
Local laboratory assessments					
Hematology ^{12, 13}	X	X	X		
Serum chemistry ¹³	X	X	X		
Coagulation panel (aPTT, INR)	X		X		
C-reactive protein	X	X	X		
Urinalysis ¹⁴	X	X ¹⁵	X		
Serum pregnancy test ¹⁶	X				
TSH, free T3, free T4	X	Every 3 rd cycle (starting at C3, C6, C9 ctd.)	X		
HIV, HBV and HCV serology ¹⁷	X				

Appendix 1

Schedule of Assessments (cont.)

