4. STATISTICAL METHODS

Categorical data (such as discontinuation reasons or adverse events) will be summarized using frequencies and percentages (including a category for missing, if appropriate). Continuous endpoints (such as durations or concentrations) will be summarized using descriptive statistics (N, mean, standard deviation, median, lower quartile, upper quartile, minimum and maximum). Other analysis methods will be specified (below) where applicable.

Study Day 1 will be defined as the first day a patient receives study medication. Baseline values are determined by the last measurement up to and including date of treatment start (Study Day 1). For statistical evaluations (e.g. descriptive summaries) of post-baseline data summarised by visit, or by visit and timepoint, only measurements at scheduled visits or timepoints are considered. If a measurement is repeated at a scheduled visit or time point, then only the latest retest result will be used in calculation of the statistical summary. All data – including from unscheduled measurements – will be included in the listings, and used in the calculation of minimum or maximum value over the course of the study, and in the potential identification of adverse events.

Any cohort that does not reach the Stage I analysis (i.e. does not reach 12 eligible and evaluable patients), will not be presented for statistical analysis per se. (This does not preclude that some or all patients within such cohorts may be included in cross-cohort analyses.)

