4.4.3 Secondary Efficacy Endpoints

Non progression rate (NPR) at 24 weeks is defined as the percentage of patients with “CR”, “CR (imputed)”, “PR”, “PR (imputed)”, “SD” or “SD (imputed)” at 24 weeks.

Week 24 occurs at Study Day 169. Allowing 20 days either side of the exact Week 24 study day, assessments that occur between Study Day 149 and Study Day 189 (inclusive) will be considered as a Week 24 assessment.

Individual patient response at 24 weeks, based on RECIST v1.1, will be categorized as “CR”, “CR (imputed)”, “PR”, “PR (imputed)”, “SD”, “SD (imputed)”, “PD”, “Death in absence of PD”, “Discontinuation in absence of PD” or “Missing” as follows:

1. any patient who recorded PD at any post-baseline tumor assessment up to Study Day 189 inclusive, will be classified as “PD”,
2. any remaining patient who died at or prior to Study Day 189 will be classified as “Death in the absence of PD”,
3. any remaining patient will be classified as “CR”, “PR”, or “SD” according to their Investigator-reported tumor assessment data that falls within the window of Study Day 149 – 189 inclusive (taking the worst case if there are two conflicting assessments within the window),
4. for a patient who does not meet any of the above criteria, but who has a nearby later assessment (up to Day 209), the patient will be classified as “CR (imputed)”, “PR (imputed)” or “SD (imputed)” according to the first tumor assessment in the extended window.

5. any remaining patient will be classified as "Discontinuation in absence of PD" if they have an End of Study date prior to Study Day 189 or, otherwise, as "Missing/Out of window".

Best overall response (BOR), based on RECIST v1.1, for an individual patient, is defined as the best overall response obtained until progressive disease, death or lost to follow up, whichever is the first, as follows:

1. CR for a patient with an overall tumour response assessment of CR at two consecutive visits at least 28 days apart. If applicable, any tumour assessment within the 28 day period must also record CR.
2. PR for a patient with an overall tumour response assessment of PR or CR at two consecutive visits at least 28 days apart without being a CR. If applicable, any tumour assessment within the 28 day period must also record PR or CR.
3. SD, for a patient with an overall tumour response assessment of SD, PR, or CR at one or more visits at least 42 days after start of study treatment, but are not a confirmed CR or PR.

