4. PD, for a patient with an overall tumour response assessment of PD at any visit, and does not meet the criteria for a BOR of CR, PR or SD.
5. Missing, for a patient with an assessment of SD, PR or CR in the first 42 days after start of study treatment and no further tumour assessments thereafter.

Best overall response will summarize the proportion of patients with each best overall response.

Overall response rate (ORR) is defined as the proportion of patients with a BOR of CR or PR.

Clinical benefit rate (CBR) is defined as the proportion of patients with a BOR of CR, PR or SD.

Duration of response (DOR), based on RECIST v1.1, is defined as the time from the first occurrence of a documented objective response (CR or PR) to the time of progression or death from any cause, whichever occurs first. For patients who do not die or experience disease progression before the end of the study or who are lost to follow-up, duration of objective response will be censored at the day of the last tumor

assessment. Note: DOR will not be analysed if there are less than 4 patients available for the analysis.

Progression-free survival (PFS), based on RECIST v1.1, is defined as the time from the first day of study treatment to the first occurrence of disease progression or death from any cause, whichever occurs first. A patient without a PFS event will be censored at the time of the last evaluable tumor assessment or, for patients with no tumor assessment after the baseline visit, at the time of the first day of study treatment plus 1 day.

Time to progression (TTP), based on RECIST v1.1, is defined as time from the first day of study treatment to the first occurrence of progressive disease or death due to disease progression, whichever occurs first. Patients who have not progressed or died due to disease progression at the time of study completion or who are lost to follow-up will be censored at the date of the last evaluable tumor assessment or, for patients with no tumor assessment after the baseline visit, at the time of the first day of study treatment plus 1 day.

Overall survival (OS) is defined as the time from the first day of study treatment to death from any cause. Patients who are still alive at the time of analysis (clinical cut-off) and patients who are lost to follow-up will be censored at the last date they were known to be alive.

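### The 24-week Kaplan-Meier PFS and TTP rates are read on the target day of the Week 24 scan, so progressions found at compliant scans after that day count as progression-free

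*SAP*

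**What the plan says.** SAP 4.4.4.3 asks for "the estimated survival rate together with its associated 95% confidence interval at 24 weeks, at 6 and 12 months", with 24 months added for OS only. It does not say on which day the curve is read.

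PFS is "the time from the first day of study treatment to the first occurrence of disease progression or death from any cause". TTP is "time from the first day of study treatment to the first occurrence of progressive disease or death due to disease progression". Both start at first dose, and SAP 4 sets that origin: "Study Day 1 will be defined as the first day a patient receives study medication".

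SAP 4.4.3 places the visit: "Week 24 occurs at Study Day 169". Protocol Appendix 1 schedules tumour assessments 6-weekly "for the first 24 weeks and every 12 weeks" thereafter, each with a tolerance of 5 days either way.

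For NPR at 24 weeks the SAP sets a wide window: "assessments that occur between Study Day 149 and Study Day 189 (inclusive) will be considered as a Week 24 assessment". Any progression recorded up to Study Day 189 counts against the patient. The Kaplan-Meier rate has no matching rule.

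Protocol 6.5.2 asks only for the median and the 1-year and 2-year rates. The 24-week landmark is an SAP addition.

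**The concern.** Progression is dated at the scan that finds it, so PFS and TTP events cluster around scan days. A landmark in the middle of a scan window splits one cluster by the accident of the appointment date. Two patients with the same disease course, scanned two days before and two days after the target, would be scored differently at 24 weeks.

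The next scheduled scan is 12 weeks later, so the whole Week 24 cluster bears on this one cut point. The protocol treats Week 24 and 6 months as the same time (sections 6 and 6.9), yet the SAP would print two Kaplan-Meier rates for it that can differ through scan timing alone. Readers are likely to use the figure: protocol 1.3.2 itself cites 24-week PFS rates from another study as evidence of activity.

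**Working it through.** **Day arithmetic.** 24 × 7 + 1 = 169, and 169 ± 20 gives 149 and 189, so the SAP's own figures are reproduced. Study Day 169 is 168 days after Study Day 1, and 24 weeks is 168 days: the landmark and the scan target coincide. With the 5-day tolerance, compliant Week 24 scans fall 163 to 173 days after first dose.

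**Scan days beyond the landmark.** A Kaplan-Meier rate at 168 days counts events at or before 168.
- Event time as a plain date difference: days 169 to 173 fall after it, 5 of 11 allowed days (45.5%).
- Event time with one day added: a scan on the target day also falls after it, 6 of 11 (54.5%).

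SAP 4.4.3 does not say which applies to PFS and TTP. SAP 4.7.1 does add a day for time on treatment.

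**Effect on the rate.** Assumptions, none of them in the documents: exponential progression, no other deaths, no censoring, and independent scan offsets d, uniform over a stated range. The 18-week progression-free rate p is set to 40% and 20%, the plan's design values for NPR.

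S(t) = p^(t/126), so the true S(168) = p^(4/3), which is 29.5% or 11.7%.

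Rate read at 168 days = (share of scans after the landmark) × mean S(126 + d) + (share at or before it) × mean S(168 + d) over those scans.

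Symmetric scans, d from −5 to +5, plain date difference:
- p = 40%: 5/11 × 0.4001 + 6/11 × 0.3002 = 0.1819 + 0.1637 = 34.6%.
- p = 20%: 5/11 × 0.2002 + 6/11 × 0.1208 = 0.0910 + 0.0659 = 15.7%.

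Once the window has closed, the same curves stand at 29.5% and 11.7%. The excess is 5.1 and 4.0 points. Simulations of the same model agreed to within about 0.1 point. Of the progressions first found at Week 24, 48% are missed (57% with one day added).

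Other scan patterns:

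| Offsets, days | p = 40% (true 29.5%) | p = 20% (true 11.7%) |
|---|---|---|
| −5 to 0 | 30.0% | 12.1% |
| all on target | 29.5% | 11.7% |
| −5 to +2 | 32.6% | 14.2% |
| −5 to +5 | 34.6% | 15.7% |
| −2 to +5 | 35.9% | 16.7% |
| all on target, one day added | 40.0% | 20.0% |

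With plain date differences the excess over these patterns runs from about 0 to about 6 points. The last row is the ceiling: the whole Week 24 drop is missed, 40.0 − 29.5 = 10.5 points.

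**In patients.** 25 × 0.051 = 1.3 and 25 × 0.040 = 1.0, so about one patient in a full cohort.

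**The 6-month landmark.** Taking 6 months as 365.25/2 = 182.6 days, it falls after the last compliant Week 24 scan under either convention (173 or 174 days). No in-window progression is missed.

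**The case against.** The strongest case against has five parts.

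1. **The scan dates are unknown.** A reader might infer that half the Week 24 progressions are lost in every cohort. The documents do not support that. With bell-shaped offsets (SD 2.5 days) shifted by −3 to +5 days, the missed share ran from about 9% to 98%. With plain date differences and every scan on target, there is no bias. This stands, so the size must be given as a range.
2. **The gap from NPR has other causes.** A reader might infer that the 24-week Kaplan-Meier rate and NPR at 24 weeks would differ only because of the cut point. They would not agree even with it repaired. NPR counts only CR, PR and SD as non-progression, so discontinued and missing patients are failures. Kaplan-Meier censors them at the last evaluable assessment, and TTP does not count deaths from other causes as events. This stands. The comparison with the 6-month rate is the cleaner one.
3. **Later readings also sit above the true curve.** Scan-detected curves stay flat between scans. In the 40% model the 6-month reading of 29.5% compares with a true 26.5% on that day, and a Study Day 189 reading compares with a true 25.5%. This stands, and it governs how the repaired figure should be labelled.
4. **The consequence is small.** The approximate 95% half-width at 34.6% with 25 patients is 1.96 × √(0.346 × 0.654/25), about 19 points. The all-cohorts-combined analysis excludes time-to-event endpoints (SAP 2.2.1), and the model leaves out deaths, whose dates do not depend on scans. This stands.
5. **Nominal landmarks are routine, and the 6-month rate is in the same sentence.** That is true, but it does not justify printing a second rate that depends on appointment dates and on an unstated one-day convention.

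**Conclusion.** The point holds as a limited defect in a descriptive secondary rate. The landmark is the target day of a scan with a symmetric tolerance, and the SAP makes an allowance for NPR at 24 weeks but not for the Kaplan-Meier rate. Under symmetric scan dates the PFS and TTP rates are about 4 to 5 points too high. Over plausible early to late patterns the excess is about 0 to 6 points. If one day is added to event time, scans exactly on target are missed too, and the excess could reach about 10 points. These sizes rest on the exponential model without censoring or other deaths, and on reading 24 weeks as 168 days, which the SAP implies but does not state.

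A reader might also infer that cohort decisions are at risk. They are not: the go/no-go rule uses NPR at 18 weeks. OS is unaffected because deaths are not dated by scans. DOR starts from a different origin and is outside this point. The change is worth making because it is nearly free, but no conclusion of the trial depends on it.

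**What to change.** In SAP 4.4.4.3, for PFS and TTP, drop the separate 24-week landmark and keep the 6-month rate already in the same sentence. Nothing the protocol requires is lost.

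Alternatively, report the Kaplan-Meier estimate after the Week 24 assessment, read at the close of the SAP's own window (Study Day 189). Label it as the Week 24 assessment rate, not as a Day 189 rate, because it would be too high for that day. This option also covers scans outside the 5-day tolerance: if scans were spread evenly over the SAP's 20 days either side, 12% to 17% would still fall after 6 months, but none after Study Day 189.

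In either case, state in SAP 4.4.3 whether PFS and TTP event times add one day. OS can keep its 24-week rate.

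The cost is a line or two of SAP text and one programming parameter. The downside is that the 24-week PFS and TTP rates disappear or become slightly less favourable.

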4.5 PHARMACOKINETIC (PK) ANALYSIS

The PK analysis will be performed on the safety population. Atezolizumab serum concentration data will be summarized descriptively, for each cycle and timepoint at which PK is measured. Descriptive statistics will include the numbers of patients below the limit of quantification (BLQ), mean, SD, median, minimum and maximum.

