1.2.5 Clinical Pharmacokinetics

On the basis of available preliminary PK data (0.03–20 mg/kg), Atezolizumab appeared to show linear pharmacokinetics at doses \geq 1 mg/kg. For the 1-mg/kg and 20-mg/kg dose groups, the mean apparent clearance (CL) and the mean volume of distribution at steady state (V_{ss}) had a range of 3.11 to 4.14 mL/kg and 48.1 to 67.0 mL/kg, respectively, which is consistent with the expected profile of an IgG1 antibody in humans.

The development of anti-therapeutic antibodies (ATAs) has been observed in patients in all dose cohorts and was associated with changes in pharmacokinetics for some patients in the lower dose cohorts (0.3, 1, and 3 mg/kg). The development of detectable ATAs has not had a significant impact on pharmacokinetics for doses from 10 to 20 mg/kg. Patients dosed at the 10-, 15-, and 20-mg/kg dose levels have maintained the expected target trough levels of drug despite the detection of ATAs. To date, no clear relationship between detection of ATAs and adverse events or infusion reactions has been observed.

See the Atezolizumab Investigator's Brochure for additional details on clinical pharmacokinetics.

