5.1.3 Atezolizumab Dose Modification

There will be no dose reduction for Atezolizumab in this study. Patients may temporarily suspend study treatment if they experience adverse events that require a dose to be held. If Atezolizumab is held because of adverse events for > 105 days beyond when the next dose would have been given, then the patient will be discontinued from Atezolizumab treatment and will be followed for safety and efficacy as specified in the Schedule of Assessments ([Appendix 1](#)).

If a patient must be tapered off steroids used to treat adverse events, Atezolizumab may be held for additional time beyond 105 days. The acceptable length of interruption will depend on an agreement between the investigator and the Medical Monitor.

Dose interruptions for reason(s) other than adverse events, such as surgical procedures, may be allowed with Medical Monitor approval. The acceptable length of interruption will depend on agreement between the investigator and the Medical Monitor.

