6.7 PHARMACOKINETIC ANALYSES

Atezolizumab serum concentration data (C_{\min} and C_{\max}) will be tabulated and summarized for each cycle at which pharmacokinetics are measured (C_{\max} will be reported for Cycle 1 only; C_{\min} will be evaluated at Cycles 1, 2, 3, 4, 8, every eight cycles thereafter and at treatment discontinuation). Descriptive statistics will include means, medians, ranges and SDs, as appropriate.

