4.7.1 Exposure to Study Medication

Number of infusions will be summarized by descriptive statistics. Time on treatment (last dose date minus first dose date, plus 1, expressed in weeks), and total dose received will be summarized.

Missed treatment cycles are not recorded as such in the eCRF (sequential visits are labelled with sequential cycle number regardless of length of time between visits). Therefore to capture “missed doses” and delayed dose irregularities we categorize

- *Patients with one or more missed cycle* as being patients who have ≥ 42 days between two consecutively labelled cycles (target cycle time being 21 days)
- *Patients with at least one cycle delayed by 10 days or more* (i.e. ≥ 31 days between two consecutively labelled cycles). Patients with one or more missed cycle as just defined are also included in this category.

We also present total patient years of exposure to Atezolizumab (per cohort, and across the study) calculated as the sum of individual time on treatment (last day of treatment minus first day of treatment plus one day), expressed in years (i.e. days/365.25).

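### Pre-dose concentrations are summarised by sequential cycle number without regard to time since the last infusion, so samples after missed or held doses are pooled with on-time three-weekly troughs

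*SAP*

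**What the plan says.** SAP 4.5 plans, on the safety population, that "Atezolizumab serum concentration data will be summarized descriptively, for each cycle and timepoint at which PK is measured". The statistics are the number below the limit of quantification, mean, SD, median, minimum and maximum. The section sets no window or exclusion based on the time since the previous infusion.

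Protocol 6.7 states that C_min "will be evaluated at Cycles 1, 2, 3, 4, 8, every eight cycles thereafter and at treatment discontinuation". Protocol 4.3.2 sets the planned interval at 21 days, plus or minus 3.

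SAP 4.7.1 explains how cycles are labelled: "Missed treatment cycles are not recorded as such in the eCRF", and "sequential visits are labelled with sequential cycle number regardless of length of time between visits". For the exposure summary only, the SAP works around this by using the gap between visits. It flags a delay at "≥ 31 days between two consecutively labelled cycles" and a missed cycle at 42 days or more.

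Long gaps are allowed. Protocol 5.1.3 requires discontinuation only "If Atezolizumab is held because of adverse events for > 105 days beyond when the next dose would have been given". It leaves longer interruptions, for a steroid taper or for reasons other than adverse events, to agreement with the Medical Monitor.

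**The concern.** A reader of a C_min table will take each row as the pre-dose level under dosing every three weeks, because Protocol 3.3.1 discusses the regimen in terms of that trough. Under sequential labelling, a Cycle 4 pre-dose sample could follow the previous infusion by 21, 42 or 126 days and still sit in the Cycle 4 row. The SAP sees the labelling problem and corrects for it in the exposure summary, but does not carry the correction into the PK summary.

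The rows are small. SAP 2.2.1 leaves PK out of the all-combined analysis, so these tables exist only per cohort, and cohorts are planned at 12 to 25 evaluable patients. One late sample is then 1/25 = 4% to 1/12 = 8% of a full row. The mean, the minimum and the count below quantification respond to a few low values. At stake is how well the table describes the regimen for the PK objective.

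**Working it through.** The plan states no figure on this point to reproduce. Its thresholds agree with its own 21-day target: 21 + 10 = 31 days and 2 × 21 = 42 days. The longest gap under the basic rule in Protocol 5.1.3 is 21 + 105 = 126 days.

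**Inputs.** Protocol 1.2.5 says that mean clearance and volume at steady state "had a range of 3.11 to 4.14 mL/kg and 48.1 to 67.0 mL/kg, respectively". Clearance is printed without a time unit; mL/kg per day is assumed. One-compartment decay is assumed. The average weight-based dose of 15 mg/kg is from Protocol 3.3.1. Half-lives of 27 and 30 days are added as assumed sensitivity values.

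**Step 1, half-life** = 0.693 × V / CL.
- Shortest: 0.693 × 48.1 / 4.14 = 8.05 days.
- Longest: 0.693 × 67.0 / 3.11 = 14.9 days.

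**Step 2, ratio of a late sample to the on-time trough** = 2^(−(d − 21)/half-life), with d the days since the previous infusion. At 42 days: 2^(−21/8.05) = 0.16, 2^(−21/14.9) = 0.38, 2^(−21/27) = 0.58 and 2^(−21/30) = 0.62.

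**Step 3, modelled Cycle 4 pre-dose level**, adding dose/V at each infusion and decaying by exp(−(CL/V) × interval), with only the last interval lengthened. The ranges cover all four combinations of the CL and V limits.

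| Last interval (days) | Ratio, protocol CL and V | Ratio, 27-day half-life | Cycle 4 level, protocol CL and V (µg/mL) |
|---|---|---|---|
| 21 | 1 | 1 | 61–128 |
| 31 | 0.42–0.63 | 0.77 | 26–81 |
| 42 | 0.16–0.38 | 0.58 | 10–48 |
| 63 | 0.03–0.14 | 0.34 | 1.6–18 |
| 126 | below 0.01 | 0.07 | 0.01–1.0 |

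The lowest 42-day value at Cycle 2 is (15000/48.1) × exp(−42 × 4.14/48.1), about 8.4 µg/mL.

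**Step 4, fall in the row mean** = f × (1 − ratio), with f the share of late samples. The documents do not give f, so a range is shown.

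| f | All late samples at 31 days | All late samples at 42 days |
|---|---|---|
| 5% | 2%–3% | 3%–4% |
| 10% | 4%–6% | 6%–8% |
| 20% | 7%–12% | 12%–17% |
| 30% | 11%–17% | 19%–25% |

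With a 27-day half-life and 42-day gaps, the fall is 0.10 × 0.42 = 4% at f = 10% and 0.20 × 0.42 = 8% at f = 20%.

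**Step 5, possible safeguards elsewhere.** SAP section 4 limits by-visit summaries to scheduled visits, but a late Day 1 of the next numbered cycle is still a scheduled visit. Protocol Appendix 2 sets a window of plus or minus 1 day around Day 1 of the sampled cycles after Cycle 1. It does not tie that window to the previous infusion, and no text drops a sample that falls outside it. Neither rule removes held-dose samples.

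**The case against.** **The protocol specifies this summary.** Protocol 3.4.3 and 6.7 define C_min as the pre-infusion level at named cycles, not as the level after exactly 21 days. An as-treated summary by cycle follows that definition. This stands, and it is why the planned rows should stay and the windowed rows should be an addition.

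**The link to the eCRF label is inferred.** SAP 4.5 does not name its source for cycle. True, but 4.7.1 is the only account of cycle numbering in the SAP.

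**The size rests on assumptions.** The clearance unit, the one-compartment model and the share of late samples are all assumed. This stands: the direction is firm, the size is not. Doses given up to 3 days early also push slightly the other way.

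**Stronger readings are tempting, and the documents do not support them.**
- A reader might infer that the table would make 1200 mg look unable to hold the 6 µg/mL target. One skipped cycle still models above 6 µg/mL (10 to 48 at Cycle 4, 8.4 at worst at Cycle 2). Values below it need much longer gaps, whose frequency is not given, and the SAP plans no comparison with 6 µg/mL.
- A reader might infer that the dose choice rests on this table. Protocol 3.3.1 bases it on nonclinical data and Study PCD4989g, and refers continued evaluation to all available data on the drug.
- A reader might infer confusion with an antibody effect. SAP 4.5 and 4.6 plan no table of concentration by antibody status.
- A reader might infer that discontinuation-visit and Cycle 1 pre-dose samples contaminate the troughs. They are separate sampling occasions, and nothing says they are averaged into another row.

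**A window alone would select patients.** Keeping only on-time samples drops those held for toxicity. This also stands, and the fix allows for it.

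**Conclusion.** The concern holds as a limited point about a descriptive analysis. As written, SAP 4.5 pools pre-dose samples taken after held or missed doses with on-time three-weekly troughs. The mean and minimum in each cohort row are then too low as a description of the three-weekly regimen. The count below quantification can only be raised; by how much cannot be stated, because the assay limit is not given. The median moves little if few samples are late. The Cycle 1 samples are not affected.

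A sample at 42 days reads about 16% to 38% of the on-time trough under the protocol's clearance and volume with the assumptions above, and about 58% to 62% with a half-life of 27 to 30 days. If 10% to 20% of a row's samples followed a 42-day gap, the row mean would fall by 6% to 17%; that share is an assumption.

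Nothing here touches the non-progression rate, its type I error, the Stage I or Stage II rules or the choice of dose. The change is worth making because the SAP already recognises the labelling problem and the remedy is cheap.

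**What to change.** In SAP 4.5:
- Derive the actual time since the previous infusion for each pre-dose sample from the recorded dates.
- Keep the planned all-sample summary by cycle.
- Add a three-weekly trough summary for Cycles 2, 3, 4, 8 and each eighth cycle after that, limited to samples taken 18 to 24 days after the previous infusion, which is the protocol's own 21 ± 3 day cycle.
- Summarise the other pre-dose samples by time since last dose.

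Within that window the remaining timing error per sample is roughly two-sided: −13% to −23% at 24 days and +15% to +30% at 18 days, on the protocol's clearance and volume.

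The cost is one derived variable, a few sentences and slightly more output. The SAP already measures gaps between cycles in 4.7.1, so no new data are needed. The windowed rows will hold fewer samples and will under-represent patients held for toxicity, which is why the all-sample rows stay. Relabelling the Cycle 1 pre-dose sample as baseline and reporting the percentage below 6 µg/mL are optional and not needed for this correction.
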